#### **NT-proBNP, troponin, LVEF – 8 weeks**

#### Hypothesis

For each of the main safety measures (NT-proBNP, troponin and LVEF), it will be assessed whether there is a difference in the change of the measurement following an additional 4 week period of elevated night pacing after an initial 4 week period of elevated night pacing compared to that period of 4 weeks with the elevated night pacing programmed OFF after the initial 4 weeks period of elevated night pacing.

#### Analysis Methods

A paired comparison of the measurement at the 8 week visit compared to the measurement at the 4 week visit period compared to the value at the start of the period will be calculated. A two-sided paired t-test will be performed testing the hypothesis

$$H_0: \mu_{ON} = \mu_{OFF}$$

$$H_a: \mu_{ON} \neq \mu_{OFF}$$

Where  $\mu_{ON}$  = difference in NT-proBNP, troponin or LVEF from week 4 to week 8 for subjects in the ON arm and  $\mu_{OFF}$  = difference in those measurements in subjects in the OFF arm

SAS code similar to the following will be used to evaluate the 8 week ancillary safety endpoints, where the variables in the VAR statement will equal the difference between the 8 week and 4 week measurements:

```
PROC TTEST;
  CLASS trt;
  VAR ntpobnppdiff;
RUN;

PROC TTEST;
  CLASS trt;
  VAR troponindiff;
RUN;

PROC TTEST;
  CLASS trt;
  VAR lvefdiff;
RUN;
```

An ANCOVA model may also be used for all analyses prospectively planned as T-tests, in addition to the T-tests for this and other similar ancillary objectives comparing the 4 and 8 week data by randomized treatment group. ANCOVA models may be implemented using SAS code similar to

```
PROC GLM;
  CLASS trt;
  MODEL ntpobnppdiff= trt ntpobnpp0;
  LSMEANS trt / pdiff cl alpha=0.05;;
RUN;
```

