### 10.11. Randomization (4 Week Follow-Up)

Subjects will be assigned to a group at random during the randomization visit. Randomization will occur at 4 weeks.

Subjects will be randomized in a 2:1 ratio to the Elevated Night Pacing ON or to the Elevated Night Pacing OFF group.

Sites will receive this randomization assignment from the randomization schedule, which is automatically populated on the eCRF.

Procedures to be performed and data to be collected at Randomization include:

- Physical Assessment (including weight, heart rate, symptoms, and blood pressure)
- Medications
- NYHA Class
- MN Living with Heart Failure Questionnaire
- 6 Minute Walk Test
- Echo\*
- Blood Draw\*\*
- Randomization assignment
- Device Interrogation/ (initial)
- Save-to-Media (initial)
- Device Programming, see Table 7: Programming Recommendations at 4 Week Follow-Up
- Device Interrogation (final) - this needs to be completed at the end of the visit after programming has been completed
- Save-to-Media (final)
- Adverse Events (report new/assess ongoing AEs), Study Deviations, System Modifications, Device Deficiencies, Crossovers (as they occur)

\*The echo must be sent to the Echo Core Laboratory for analysis, with a copy of the echo remaining at the site. Details of the Echo Core Laboratory, type of echo to be performed, and the review process will be provided in an Echocardiography Handbook (provided under separate cover).

\*\* The blood sample must be sent to the Blood Core Laboratory for analysis. Details of the blood core lab and the blood draw process will be provided under separate cover.

For any subject who has an abnormal NT-proBNP, troponin or LVEF measurement as defined in the Safety Assessment (Section 10.19. Assessment of Safety) and the investigator elects to discontinue elevated night pacing, a subsequent visit will be necessary for the elevated night pacing to be programmed OFF if the subject was randomized to the elevated pacing ON arm. The subject should continue to be followed through the 12 week visit.

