### 13.2. Blood Core Laboratory

[figure not shown]
The study will utilize a Blood Core Laboratory (blood core lab). The blood core lab will complete data analysis on all study blood samples required to be performed (Baseline, 4 week, 8 week, and 12 week). Details of the blood core lab and the blood draw process will be provided under separate cover.

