## 5.3. Study Procedures

Clinical data is collected at designated time points throughout the study as indicated in Table 1 below. Data will be collected using eCRFs, an electronic data management system for clinical studies. At the baseline, 4 week, 8 week, and 12 week visits subjects are to fill out the MN Living with Heart Failure Questionnaire and perform a 6 Minute Walk Test. At the same visits, an echocardiogram must be done, for which instructions are provided in an Echocardiography Handbook (provided under separate cover). A blood draw must also be done, (instructions are provided under separate cover.) The device programming should occur after all other study procedures are complete, except for the final device interrogation and save-to-media. The EQ-5D-5L Questionnaire will only be collected at the Baseline and 8 week visits.

In addition to eCRF data, non-eCRF data will be collected to include device interrogation files/save-to-media and digital echo data.

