###### Analysis Methods

A paired comparison of the value at the end of the period compared to the value at the start of the period will be calculated. A two-sided paired t-test will be performed testing the hypothesis

$$H_0: \mu = 0$$

$$H_a: \mu \neq 0$$

Where  $\mu$  = difference in measurement from baseline to week 4 visit

SAS code similar to the following will be used to evaluate the 4 week ancillary safety endpoints:

```
PROC TTEST;
  PAIRED ntprobp0*ntprobp4;
RUN;

PROC TTEST;
```

```
PAIRED troponin0*troponin4;  
RUN;  
  
PROC TTEST;  
  PAIRED lvef0*lvef4;  
RUN;
```

By default, subjects that do not have 4 week measurements available will be excluded from the analysis.

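### The optional ANCOVA for the week 4-to-8 change adjusts for the week-0 value rather than the week-4 value, so it gives up all or part of the available precision gain

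*SAP*

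**What the plan says.** Protocol 10.11 sets the time of allocation: "Randomization will occur at 4 weeks". In SAP 7.9.2, under the 8-week analysis of NT-proBNP, troponin and LVEF, the outcome is defined so that "the variables in the VAR statement will equal the difference between the 8 week and 4 week measurements". The planned test is a two-group t-test on that difference.

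The same section then permits an ANCOVA alongside the t-tests, for this endpoint and for the similar ones that compare week-4 and week-8 data by arm. The only code given is "MODEL ntpobnppdiff= trt ntpobnpp0". No text names or justifies the covariate.

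The meaning of the suffix comes from the 4-week analysis in the same section. The code "PAIRED ntprobp0*ntprobp4" goes with a parameter defined as the "difference in measurement from baseline to week 4 visit". So 0 denotes baseline and 4 denotes week 4. The paired code for troponin, LVEF, MNLWHF, walk distance and EQ-5D-5L uses 0 for baseline in the same way.

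The week-4 value is available. Protocol 10.11 lists blood draw, echo, MNLWHF and walk test at the randomisation visit, and SAP 5.3 states: "The device programming should occur after all other study procedures are complete".

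**The concern.** The arms are treated alike until week 4. Every subject has elevated night pacing between week 0 and week 4, and the study hypothesises that this changes the measures being analysed. The week-0 value therefore does not describe the state from which the arms diverge. The week-4 value does, and it is also the subtracted term in the outcome. A subject who is high at week 4 by chance tends to fall by week 8 whatever the arm, and a week-4 covariate is what absorbs this.

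The contrast matters within the study. Protocol Section 14 treats the ON versus OFF comparison from week 4 to week 8 as the one that can indicate a real therapeutic effect, because the first four weeks are single-arm and unblinded. Under SAP 4.2 and 7.9.8, a nominally significant result there leads to the week-12 sustained-effect tests. With 2:1 allocation and about 30 subjects, chance imbalance at week 4 is likely to be noticeable.

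**Working it through.** The plan states no power, SD, visit correlation or effect size for this comparison, so it has no figure to reproduce.

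**Inputs from the documents.** Outcome D = Y8 − Y4; randomisation at week 4; 2:1 allocation; 30 subjects paced, hence at most 20 ON and 10 OFF if all reach randomisation.

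**Assumptions not in the documents.** Equal variance (1 SD²) at weeks 0, 4 and 8; adjacent-visit correlation r from 0.5 to 0.9; the week 0-to-8 correlation is either r (equal correlation) or r² (AR(1)).

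**Step 1. Unadjusted.** Var(D) = 2(1−r).

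**Step 2. Week-4 covariate.** Cov(D, Y4) = −(1−r). Residual variance = 2(1−r) − (1−r)² = (1−r)(1+r). Ratio to unadjusted = (1+r)/2.

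**Step 3. Week-0 covariate.**
- Equal correlation: Cov(D, Y0) = r − r = 0, so the ratio is 1.
- AR(1): Cov(D, Y0) = r² − r = −r(1−r), so the ratio is 1 − r²(1−r)/2. The week-4 gain is (1−r)/2, so week 0 recovers a share r² of it.

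**Step 4. Shift in the estimate per 1 SD of week-4 imbalance.**
- t-test, or week-0 covariate under equal correlation: −(1−r).
- Week-0 covariate under AR(1): −(1−r)(1−r²).
- Week-4 covariate: 0.

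| r | Variance ratio, week 4 | Variance ratio, week 0, equal corr. | Variance ratio, week 0, AR(1) | Shift, t-test or week 0 equal corr. | Shift, week 0 AR(1) |
|---|---|---|---|---|---|
| 0.5 | 0.750 | 1.000 | 0.938 | −0.500 | −0.375 |
| 0.7 | 0.850 | 1.000 | 0.926 | −0.300 | −0.153 |
| 0.8 | 0.900 | 1.000 | 0.936 | −0.200 | −0.072 |
| 0.9 | 0.950 | 1.000 | 0.960 | −0.100 | −0.019 |

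Before the small cost of estimating a slope, the week-4 covariate makes 30 subjects worth 30/0.75 = 40.0 at r = 0.5 and 30/0.90 = 33.3 at r = 0.8. The share recovered by week 0 under AR(1) is 25% at r = 0.5, 49% at 0.7, 64% at 0.8 and 81% at 0.9. With a week 0-to-8 correlation midway between r and r², it is 6% to 20% over r = 0.5 to 0.9.

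**Step 5. How large an imbalance to expect.** At 20:10 the SE of the week-4 difference is √(1/20 + 1/10) = 0.387 SD, and the chance of an imbalance above 0.5 SD is about 20%. A one-SE imbalance moves the unadjusted contrast by 0.5 × 0.387 = 0.19 SD at r = 0.5 and by 0.2 × 0.387 = 0.08 SD at r = 0.8.

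**Step 6. Simulation, 20:10, 20,000 runs per setting.** Variance relative to the t-test:

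| Structure, r | Week-0 covariate | Week-4 covariate |
|---|---|---|
| Equal, 0.6 | 1.040 | 0.823 |
| Equal, 0.7 | 1.036 | 0.876 |
| Equal, 0.8 | 1.038 | 0.937 |
| AR(1), 0.6 | 0.967 | 0.839 |
| AR(1), 0.7 | 0.959 | 0.880 |
| AR(1), 0.8 | 0.979 | 0.945 |

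The ratios sit slightly above the formulas because one slope must be estimated from 30 subjects. Under equal correlation the week-0 model is about 4% worse than no adjustment. At r = 0.7, the slopes of the estimate on week-4 imbalance matched Step 4: −0.30 (t-test), −0.30 (week 0) and 0.00 (week 4) under equal correlation; −0.30, −0.15 and 0.00 under AR(1).

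**The case against.** The best counter-argument is that little rests on this model. It is an optional supplement, the code is only indicative, and the planned test is the t-test. The study is exploratory and unpowered, and SAP Section 6 names the 4-week safety and tolerability objective, which does not use this model, as what helps decide whether to proceed. All of this stands and limits the weight of the point. It does not make week 0 the right covariate.

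Four stronger readings are tempting and are not supported:

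- **That the SAP commits to this model for every 4-to-8-week endpoint.** It permits the model and does not require it.
- **That the estimate is biased or invalid.** Week 0 is also a pre-randomisation value, so adjusting for it is legitimate and the estimate is unbiased over randomisation. The shifts in Step 5 are conditional on an imbalance. The SE of the change contrast is √(2(1−r)) × 0.387, or 0.39 SD at r = 0.5 and 0.24 SD at r = 0.8. A one-SE imbalance therefore moves the estimate by about half and about a third of an SE, and the t-test interval already allows for this variation.
- **That week 0 achieves nothing.** This is exact only under equal correlation. Under AR(1) at r = 0.9 the gap between the two covariates is about one percentage point of variance (4% against 5%).
- **That EQ-5D-5L has the same fault.** It is collected only at baseline and week 8 and analysed as change from baseline, so week 0 is its matching covariate.

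One could also read the suffix 0 as the start of the 4-to-8-week period. The SAP's other code uses 0 for study baseline throughout, so this is unlikely, but the spelling of the NT-proBNP variable differs between the two code blocks and no text settles it.

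**Conclusion.** The mismatch is clear from the documents: the outcome starts at week 4, allocation is at week 4, and the template covariate is from week 0. If the ANCOVA is run as written, it gives up all of the available precision gain under equal correlation and a share 1 − r² of it under AR(1). The available gain is a variance reduction of 25% at r = 0.5, falling to 5% at r = 0.9. In every structure examined, the week-4 covariate was at least as precise and removed the dependence on week-4 imbalance.

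The covariate mismatch is certain. The sizes are illustrative: they assume r, equal variances and approximate normality, and NT-proBNP and troponin may be skewed. The 20:10 split is the best case, since subjects who leave before week 4 are not randomised. This is a modest improvement to a supplementary analysis of the study's only randomised contrast, not a threat to its validity.

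**What to change.** In the ANCOVA template of SAP 7.9.2, replace the week-0 covariate with the week-4 value, and say in the text that it is the value from the randomisation visit. Apply this to every week 4-to-8 t-test comparison with a week-4 measurement: NT-proBNP, troponin, LVEF, MNLWHF, walk distance, continuous echo measures and biomarkers. Keep week 0 for EQ-5D-5L. Week 0 may be added as a second covariate if wanted.

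A separate, secondary suggestion is to state in advance whether the adjusted estimate will be reported beside the t-test, so that the choice does not follow the results.

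The cost is one variable name and a sentence in the SAP. The week-4 values are already scheduled for collection.

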#### Determination of Subjects for Analysis

All subjects that completed 4 weeks of elevated night pacing. NT-proBNP, troponin or LVEF at time of exit will be used for subjects that do not complete the full 4 weeks of participation in the study from week 4 to week 8.

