	
 
• Adverse Events (report new/assess ongoing AEs), Study Deviations, System Modifications, Device Deficiencies, Crossovers (as they occur)
 
 
10 Week Telephone Call Follow Up Visit:
 
 
• Symptom Assessment
 
• Heart Rate
 
 
12 Week In-Clinic Follow Up Visit (Exit):
 
 
• Medications
 
• Physical Assessment (including weight, heart rate and blood pressure)
 
• NYHA classification
 
• MN Living with Heart Failure Questionnaire
 
• 6 Minute Walk Test
 
• Blood Draw
 
• Echo
 
• Device Interrogation (initial)
 
• Save-to-Media (initial)
 
• Device Interrogation (final) - this needs to be completed at the end of the visit after programming has been completed
 
• Save-to-Media (final)
 
• Adverse Events (report new/assess ongoing AEs), Study Deviations, System Modifications, Device Deficiencies, Crossovers
 
 
Early study exit (prior to 12 week visit):
 
 
• Date of visit
 
• Reason for exit
 
• Adverse Events (report new/assess ongoing AEs), Study Deviations, System Modifications, Device Deficiencies, Crossovers
 
• Complete a Scheduled/Unscheduled Follow Up eCRF, if applicable
 
 
Unscheduled Follow Up:
 
The following are recommended at the discretion of the investigator if deemed necessary:
 
 
• Physical Assessment (including weight, heart rate and blood pressure)
 
• Medications
 
• Echo
 
• Blood draw
 
• Device Interrogation (initial)
 
• Save-to-Media (initial)
 
• Program the Sleep Function to protocol
 

--	---

	
 
• Device Interrogation (final) - this needs to be completed at the end of the visit after programming has been completed Save to Media (final)
 
 
The following are required:
 
 
• Adverse Events (report new/assess ongoing AEs), Study Deviations, System Modifications, Device Deficiencies, Crossovers
 

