### Determination of Subjects for Analysis

All subjects that completed 4 weeks of elevated night pacing. MNLWHF scores at time of exit will be used for subjects that do not complete the full 4 weeks of participation in the

study from week 4 to week 8. MNLWHF questionnaire responses will only be included if at least 17 of the 21 questions are completed at both 4 and 8 weeks.

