#### Determination of Subjects for Analysis

All subjects that completed 8 weeks of elevated night pacing. Subjects that were unable to tolerate or withdrew from the treatment during the first 4 weeks because of safety or other issues will not be included in this efficacy analysis. EQ-5D-5L questionnaire responses will only be included if all 5 questions were answered at baseline and 8 weeks. EQ-5D-5L score at time of exit will be used for subjects that do not complete the full 4 weeks of participation in the study from week 4 to week 8.

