## Determination of Subjects for Analysis

All subjects that completed 8 weeks of elevated night pacing. Subjects that were unable to tolerate or withdrew from the treatment during the first 4 weeks because of safety or other issues will not be included in this efficacy analysis. EQ-5D-5L scores at time of exit will be used for subjects that do not complete the full 4 weeks of participation in the study from week 4 to week 8. EQ-5D-5L questionnaire responses will only be included if all 5 questions were answered at baseline and 8 weeks.

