### Determination of Subjects for Analysis

All subjects that completed 4 weeks of elevated night pacing. 6 Minute Walk Test distance at time of exit will be used for subjects that do not complete the full 4 weeks of participation in the study from week 4 to week 8. Subjects that did not take the 6 Minute Walk Test at either week 4 or 8 will be assigned a distance of 0 for the missed visit. A sensitivity analysis may be done excluding subjects instead of assigning a distance of 0.

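### The week-8 analyses rely on values taken at study exit, but no questionnaire or walk test is scheduled at exit, and the SAP's completeness and 0 m rules conflict with the exit-value rule

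*SAP*

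**What the plan says.** SAP 7.4 rules out imputation unless an endpoint's own methods say otherwise. The week-8 subsections do say otherwise. SAP 7.9.2: "NT-proBNP, troponin or LVEF at time of exit will be used for subjects that do not complete the full 4 weeks". SAP 7.9.4: "MNLWHF scores at time of exit will be used for subjects that do not complete the full 4 weeks" and "EQ-5D-5L scores at time of exit will be used for subjects that do not complete the full 4 weeks". SAP 7.9.5: "6 Minute Walk Test distance at time of exit will be used for subjects that do not complete the full 4 weeks". SAP 7.9.6 and 7.9.7 have matching sentences for echo and collagen biomarkers. Protocol 14.1.2 and 14.1.4 to 14.1.7 carry the same rule.

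The SAP adds further rules that are not in Protocol 14.1. MNLWHF responses will "only be included if at least 17 of the 21 questions are completed at both 4 and 8 weeks". EQ-5D-5L responses will "only be included if all 5 questions were answered at baseline and 8 weeks". A walk test not taken at week 4 or week 8 is given a distance of 0, with an optional sensitivity analysis that excludes those subjects.

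On collection, the Early Study Exit column (Protocol Table 4, SAP Table 1) marks medications, device interrogation with save-to-media, and optional programming. It is blank for both questionnaires, the walk test, echo and blood draw. The Synopsis entry that begins "Early study exit (prior to 12 week visit" asks for the visit date, the exit reason, event and deviation reporting, and a follow-up form where applicable. Protocol 10.15 is similar. Protocol 10.13 leaves echo and blood draw at an unscheduled visit to the investigator and lists no walk test or questionnaire. SAP 5.3 limits EQ-5D-5L to baseline and week 8.

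**The concern.** A dropout rule has to name a value that the study will collect. Here the SAP names one that the schedule does not produce for three endpoints and produces only at the investigator's discretion for the others. It then adds neighbouring sentences that treat the same subject differently. Two analysts following the text could count different subjects, or give one subject very different values, and each could cite the SAP.

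Protocol Section 14 treats the ON versus OFF change from week 4 to week 8 as the evidence of a real treatment effect, because the first four weeks are single-arm and unblinded. With arms this small, the handling of one or two exits can be visible in that comparison.

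**Working it through.** The plan gives no dropout rate, SD or effect size for these comparisons, so there is no stated figure to reproduce. The check sets rule against schedule and then shows the sensitivity.

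**1. Is there a planned source for the exit value?** Between weeks 4 and 8 the only scheduled contact is the 6-week phone call.

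| Week-8 endpoint | Early Study Exit | Unscheduled visit | Other SAP rule that applies |
|---|---|---|---|
| MNLWHF | blank | not listed | 17 of 21 items needed at weeks 4 and 8 |
| EQ-5D-5L | blank | not listed | all 5 items needed at baseline and week 8 |
| Walk test | blank | not listed | untaken test scored 0 m |
| NT-proBNP, troponin, biomarkers | blank | discretionary | none |
| LVEF, other echo | blank | discretionary | none |
| Device activity | interrogation marked | discretionary | none; the exit rule works |

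**2. A subject who leaves at week 6.**
- MNLWHF: the exit sentence includes the subject; the completeness sentence excludes the subject for want of a week-8 form. This holds even if a site did collect a form at exit.
- EQ-5D-5L: the same conflict. No week-4 form exists either, so baseline is the only planned value. The analysis set is also worded as subjects who completed 8 weeks of elevated pacing.
- Walk test: with no exit walk, the next applicable sentence assigns 0 m.
- Blood and echo: an exit value is used if one was taken. If not, the difference is missing and the subject drops out of the t-test. The SAP sets no time window, so a value taken days after randomisation enters the same difference variable as a full 4-week change.

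**3. Walk test arithmetic.** Planned number paced is 30, allocation 2:1. If all 30 are randomised, ON = 30 × 2/3 = 20 and OFF = 30 × 1/3 = 10. Let D be the leaving subject's week-4 distance, assumed to be 250-400 m. Scored 0 m, that subject's change is 0 − D. Against a change of zero for that subject, the arm mean moves by −D/n:
- ON: 250/20 = 12.5 m; 400/20 = 20 m
- OFF: 250/10 = 25 m; 400/10 = 40 m

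An ON exit lowers the ON minus OFF difference by that amount; an OFF exit raises it. Excluding the subject gives the same contrast when the rest of the arm averages no change.

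**4. How many exits?** Assumed exit rates of 5%, 10% and 20% between weeks 4 and 8 give 1, 2 and 4 expected exits in ON, and 0.5, 1 and 2 in OFF.

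**5. Blood and echo, illustration only.** Assume 4 ON exits, 2 of them with a 2 SD rise, and no change in anyone else. The ON mean change is:
- all exits measured: (2 × 2)/20 = 0.20 SD
- only the 2 with a rise measured: 4/(20 − 4 + 2) = 4/18 = 0.22 SD
- no exit value used: 0/16 = 0.00 SD

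In this case the rule as written comes close to the full-data answer, and discarding exit values removes the signal.

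**The case against.** The strongest reply concerns blood and echo. The follow-up form at exit and the unscheduled visit give those values a documented, though discretionary, route. Where none was taken, SAP 7.4 leaves an ordinary observed-case analysis. A reader might infer that the rule is unworkable for every endpoint; for blood and echo the documents do not support that. A reader might also infer that exit samples would come mainly from symptomatic subjects, and so differ by arm. That is plausible, since sampling is at the investigator's discretion and intolerable symptoms are a listed exit reason, but nothing in the documents says who would be sampled or how many would leave.

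Other points in the plan's favour also stand. The exposed group may be small: Protocol 10.15.4 discourages withdrawal and prefers to keep randomised subjects, and Protocol 10.11 keeps in follow-up those whose pacing is stopped after abnormal week-4 safety values. The 0 m sentence speaks of a missed visit, so applying it to study exits is a natural reading but not an explicit instruction. The SAP also allows a sensitivity analysis without the zeros, though only as an option.

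None of this supplies a planned exit questionnaire or walk, or removes the clash between the exit sentences and the week-8 completeness rules.

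**Conclusion.** The inconsistency is real and should be resolved before unblinding. For MNLWHF, EQ-5D-5L and the walk test, the exit-value rule has no planned data source. For the two questionnaires it is contradicted by the completeness rules. For the walk test, one exit read under the 0 m rule moves an arm's mean change by 12.5-20 m (ON) or 25-40 m (OFF). Those figures assume a 20:10 split and a week-4 distance of 250-400 m; neither the distance nor the exit rate is in the documents.

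For blood and echo the point is narrower: values are discretionary, have no time window, and their number and timing should be visible. It may be tempting to conclude that these exit values should be deleted. The documents do not support that: NT-proBNP, troponin and LVEF are the plan's main safety measures, and deletion could hide harm in subjects who left because of it.

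All affected endpoints are ancillary in an unpowered feasibility study. The 4-week tolerability proportion, which is to guide the decision to proceed, is untouched.

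**What to change.** **MNLWHF, EQ-5D-5L and walk distance.** Choose one:
- Mark all three in the Early Study Exit column, and word the completeness rules so that the form at the end of the period may be the week-8 form or, for a subject who left earlier, the exit form.
- Delete the exit-value sentence and analyse observed week-8 values by randomised arm, with the EQ-5D-5L analysis set reworded to match.

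In either case, state that the 0 m rule does not apply to subjects who have left the study.

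**NT-proBNP, troponin, LVEF, other echo measurements and biomarkers.** Keep every observed exit value. Report, by arm, how many exits have one and when it was taken. Show the week-8 comparison with and without these values.

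**Where and at what cost.** The exit-value sentences are also in Protocol 14.1, so changing the SAP text alone would leave the two documents in conflict. Make the same change in Protocol 14.1 and, if assessments are added, in Table 4; otherwise record the departure in SAP 7.10. A protocol revision needs approval under Protocol 16.5. The added collection is two short forms and a walk, a small burden on a leaving subject, and some who leave will still provide nothing. Dropping the exit rule adds no procedures but gives up any information from those who left.
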